5.2.3 A2.3: Relation between patient's characteristics and pain evolution

For each feature from the patient characteristics at V1, the correlation will be computed with the linear trend of pain evolution defined in A2.1. A p-value for non-zero correlation will be reported too, with BH correction for multiple testing. Results will be presented in Table (tab-cor-baseline-pain-evol).

5.3 A3: Prediction of treatment efficacy

A predictive model will be tuned based on the characteristics at V1 in order to predict the efficacy of each treatment on the patient. One model will be built for each treatment t, with the following design:

- Scope: patients having received treatment t on some but not all days
- Response (target): Per-patient treatment effect, as measured by the average difference of daily APS between the days with and without treatment t
- Predictors: patient characteristics at baseline

The performances of these pre-treatment models will be evaluated inside a resampling procedure. This procedure repeatedly samples 80% data to learn a predictive model whose predictive performances are assessed on the 20% remaining unseen data. In total, 200 train-test splits are performed for each treatment. The predictive model in use will be a ridge regression, as implemented by glmnet::cv.glmnet in R, with parameter alpha=0.

Table (tab-pred-perf) will report the average predictive performance on the test sets for each treatment, in terms of relevant statistics.

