14. Publication Policy	45
15. Literature and Data References	46
16. Attachments	49
16.1. Attachment 1 – Study Schedule – Enrolment at visit 1	49
16.2. Attachment 2 – Study Schedule – Enrolment and Screening at visit 1A	51
16.3. Attachment 3 – List of Definitions and Abbreviations.....	53
16.4. Attachment 4 – Protocol Amendment Summary	55
2.3 Secondary Endpoints	56
3.2 Introduction - Literature and/or Data Background	57
4.1. Description of Study Design	57
4.1.1. Screening and Enrolment Visit	60
5.1. Definitions	66
5.2. Population Recruitment.....	66
5.3. Inclusion Disease Criteria	66
5.5. Exclusion Disease Criteria	66
5.6. Exclusion Criteria	67
5.11. Discontinuation of Study	67
6.3. Concomittant Therapy.....	67
7.1. Study Patient Management and Requirements	67
7.2. Study Restrictions	68
8.2.3. Pain Disease Evaluation.....	70
8.2.4. Pain Evaluations	70
8.2.5. Quality of Life Questionnaires (QLQ) Quality-of-Life Questionnaire in 30 questions (QLQ-C30)	70
8.3. Information on General Health Status	71
8.3.1 Symptoms Monitoring	71
8.4. Study Procedure Priority Order.....	72
16.1 Attachment 1 – Study Schedule	75
16.1 Attachement 1 - Study Schedule – Enrolment at Visit 1	77
Section 16.2. Attachment 2 – Study Schedule – Enrolment at Visit 1A was added.....	79

Rationale for Protocol Amendment

Protocol T2001-01 version 1.0, An Observational Study to Collect Data Characterizing Analgesia in Patients Suffering from Bone Metastasis induced Pain. The new protocol version is version 2.0 and will be used to conduct the study in place of the preceding version.

The overall changes and rationale for the changes made to this protocol are as follows:

- Study design, study schedule and related sections were modified to give patients more flexibility to perform study procedures. Visit 1 and previous Visit 2 procedures can be performed either on the same visit or 2 different ones, allowing enrolment to take place at the first patient visit. Previous Visit 3 is now made optional. The numbering of the visits was therefore reviewed throughout the entire protocol.
- The number of questionnaires to be completed by patients during the study was decreased: QLQ-BM22 is no longer used and QLQ-C30 will only be performed twice.
- The information to be collected in the diary was also significantly decreased. Patients will only be asked to daily report APS, WPS and intake of additional rescue medication.

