3.2. INTRODUCTION - LITERATURE AND/OR DATA BACKGROUND

Pain is a significant issue in patients with advanced cancer. Bone is one of the common site for tumor metastasis development and CIBP is the most frequent types of cancer pains, which affect Quality-of-Life (QoL), mood, and is associated with increased morbidity. More than 80% of patients with cancer develop pain before death.

The most common cause of pain in cancer is bone metastasis. More than 70% of patients with bone metastasis suffer from pain (moderate and severe) (Langford et al. 2011). Bone metastasis does not only result from primary bone cancer which is relatively rare (2/1000 cancer diagnosed) compared to the other cancers but also from other cancers such as lung, breast, prostate and kidney cancers that have a strong predilection to metastasize to multiple bones at the same time. Tumor growth in bones results in many severe issues including pain, which altogether compromise the patient's functional status, QoL and survival. The majority of patients suffering from CIBP require pain treatments, in particular analgesic medications on a daily basis.

Description and Etiology of CIBP

CIBP is characterized by an “ongoing” pain and a “breakthrough” pain. Once the tumor has metastasized at the level of the bones, “ongoing” pain is observed characterized by continuous dull pain and gradually increasing in intensity with time. When the tumor grows and induces bone remodeling severe incident pain appears, also known as “breakthrough pain” (the pain “breaks through” the analgesic regime that is controlling the “ongoing pain”). This incident pain is an intermittent episode of extreme pain that occurs spontaneously, without any obvious precipitating event and that may occur many times a day. Current pain therapies address ongoing pain but largely remain ineffective to treat breakthrough pain that contributes greatly to decrease the patient's functional status as well as its QoL (Middlemiss et al. 2011).

The etiology of cancer pain remains unclear, as it is a complex pathology where symptoms are related to cellular, tissue, and systemic changes that occur during cell proliferation, invasion, and metastasis. In addition, the cancer cell produces mediators that affect other cells leading to nociception or neuropathy (Schmidt et al. 2010).

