7.2.2. OTHER RESTRICTIONS

Medications

During the study and in addition to their current analgesic treatment, patients will be permitted to supplement their analgesic treatment with rescue analgesic drugs (named rescue medication). Type and dose regimen of these rescue medications will be left at the discretion of Investigator.

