7.2.2.1. Diary

Once a day from enrolment till Visit 2, approximately at the same time of the day in the evening, patients will complete their diary.

The following data will be recorded:

- pain intensity assessment by recording APS and WPS for the last 24 hours (from enrolment till Visit 2 or early discontinuation). See Sections 8.2.4.4 and 8.2.4.5 for further description of APS and WPS,
- any potential event that may help to understand unexpected study outcomes,
- intake of rescue analgesic treatment if any (from enrolment to Visit 2 or early discontinuation).

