8.2.4.4. Average Pain Score (APS)

The APS will measure the average pain intensity over the last 24 hours by asking the patient “Could you please indicate us how was your average pain during the last 24 hours? For this, circle the most descriptive number on this scale.” The patient will be asked to rate it on an 11-point NRS ranging from 0 (no pain) to 10 (pain as bad as you can imagine). However, before being enrolled into the study, the patient will be asked an APS over the past week (WAPS).

8.2.4.5. Worst Pain Score (WPS):

The WPS will measure the worst pain intensity over the last 24 hours by asking the patient “Could you please indicate us how was your worst pain during the last 24 hours? For this, circle the most descriptive number on this scale.” The patient will be asked to rate it on an 11-point NRS ranging from 0 (no pain) to 10 (pain as bad as you can imagine).

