4.2 Study Participant Characteristics

The following variables will be recorded and may be used as quantitative or classification variables:

- Patient characteristics, measured at V1:
 - Study center
 - Patient's sociodemographic characteristics: age, sex and other demographic characteristics
 - Recent analgesic treatment history
 - Personality questionnaires, at facet- and domain-level: Multidimensional Health Locus of Control Scale (MHLCS, with domains I, C and P), Hospital Anxiety and Depression Scale (HADS), Revised Life Orientation Test (LOT-R) and Expectation.
 - Pain evaluation questionnaires: Douleur Neuropathique en 4 questions (DN4), Neuropathic Pain Symptom Inventory (NPSI), and Pain Catastrophizing Scale (PCS)
- Pain and quality of life assessment, measured at V1 and V2:
 - Brief Pain Inventory (BPI)
 - Quality of Life questionnaire in 30 questions (QLQ-C30), IGAC, PGAC
 - Clinical Pain Assessment (CPA): Static Allodynia (SA), Dynamic Mechanical Allodynia (DMA), Mechanical Pain Threshold (MPT), Thermal Pain Sensitivity (TPS)
- Follow-up from the daily diary and intermediate visit:
 - Daily Average and Worst Pain Score (APS and WPS),
 - Daily analgesic therapy (including rescue medication): number of distinct drugs intaken, number of distinct drug categories intaken
 - Intake of rescue analgesic treatment if any,

Note that the description of analgesic therapy hereabove requires the grouping of drugs into a small number of classes which will be described in the Statistical Analysis Report.

The collection of the values of all these variables and variables derived from them for a single patient is referred to as *the patient-vector* below in the text.

5 Description of the Analyses

The final statistical analysis covers four aspects (Ax) detailed in the following sections:

- A1: Descriptive statistics at baseline, covering secondary objectives number 1 and 2.
- A2: Evolution of daily pain and treatments, covering secondary objective number 3.
- A3: Prediction of treatment efficacy, covering the primary objective

In addition, the interim statistical analysis will cover the following two aspects, corresponding to the interim objectives:

- I1: Sample size computation for the prediction of treatment efficacy.
- I2: Relation between psychological traits and pain evolution

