The linear approximation of APS was chosen in order to describe the globally increasing or decreasing trend, while keeping easily interpretable results and avoiding overfitting. How to measure these values for one patient p:

- consider a model $APS_p(t) = a_{p0} + a_{p1} t$ where p is one patient and t is the time (in days since inclusion of patient p)
- Fit weights a_{pi} by linear regression on the patient's data (one dataset per patient, one record per timepoint)
- The variability around trend is measured by the per-patient RMSE of the linear model

Univariate statistics (mean, standard deviation (SD), median, first and third quartiles) on the distribution of these variables will be reported in Table (tab-pain-evol-distr). A one-sample Wilcoxon signed rank test will be performed in order to determine whether the linear trend in APS is globally different from zero. In addition, visualisation of the patients based on these 3 features will be performed in Figure (5).

A2.2: Summary of individual analgesic treatment evolution 5.2.2

Based on the description of analysic therapy in the patient diary, the daily number of distinct drugs will be computed as well as the daily number of distinct drug categories. Treatment doses will be ignored for this analysis. The same feature extraction as in A2.1 will be performed on these daily numbers of drugs in order to obtain a per-patient average and linear trend of the number of drugs.

Univariate statistics (mean, standard deviation (SD), median, first and third quartiles) on the distribution of these variables will be reported in Table (tab-treat-evol-distr). A one-sample Wilcoxon signed rank test will be performed in order to determine whether the linear trend in number of analgesics is globally different from zero. In addition, visualisation of the patients based on these features will be performed in Figure (6).

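### SAP 5.3 lets a rescue drug be treatment t; if rescue follows pain, its on-minus-off APS difference mixes drug effect with need and should not be read as efficacy

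*SAP*

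**What the plan says.** SAP section 5 assigns the primary objective to A3 alone. SAP 5.3 fits one model per treatment t, with the entry rule "Scope: patients having received treatment t on some but not all days". The response is each patient's mean daily APS on days with t minus the mean on days without it. The predictors are baseline characteristics, and there is no day-level adjustment. The one planned table gives average test-set performance per treatment.

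The SAP does not define t. Among the follow-up variables, SAP 4.2 lists "Daily analgesic therapy (including rescue medication): number of distinct drugs intaken". It also lists rescue intake as a separate item, and says that drugs will be grouped into a few classes to be set out in the analysis report. SAP 5.2.2 (A2.2) adds: "Based on the description of analysic therapy in the patient diary, the daily number of distinct drugs will be computed".

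The protocol's amendment rationale says of the diary: "Patients will only be asked to daily report APS, WPS and intake of additional rescue medication". Protocol 7.2.2.1 agrees: apart from the pain scores and any unusual events, it records "intake of rescue analgesic treatment if any (from enrolment to Visit 2 or early discontinuation". Under Protocol 7.2.2, rescue comes on top of current treatment, and "Type and dose regimen of these rescue medications will be left at the discretion of Investigator". On the pain score, Protocol 8.2.4.4 states: "The APS will measure the average pain intensity over the last 24 hours".

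SAP 5.4.1 (I1) reruns A3 on the interim data and on shrinking subsets to draw a learning curve, which informs the sample-size decision.

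**The concern.** As written, a rescue drug can be a treatment t. The entry rule suits drugs taken intermittently, and rescue is the only drug intake that the amended diary requires each day. Rescue drugs are therefore the ones whose on- and off-days are most directly recorded.

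A supplementary analgesic is plausibly taken on worse days. That is an inference; neither document says when rescue is taken. If it holds, on-days and off-days differ in pain for reasons other than the drug. The APS of an on-day also covers hours before the dose, including the pain that prompted it. Baseline predictors do not vary from day to day, so they cannot remove this within-patient confounding.

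At stake is the meaning of the response in the only analysis tied to the primary objective. For a rescue drug, what is labelled treatment effect would be effect plus need.

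**Working it through.** The documents give no effect size, daily SD or rescue frequency, so there is no planned figure to reproduce. Every number in steps 2 to 4 rests on assumption.

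**1. Direction.** Let Y0 be a day's pain without t, and d the true same-day effect (negative means relief). Then

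response = mean(APS | on) - mean(APS | off) = d + [E(Y0 | on) - E(Y0 | off)].

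If t is taken on worse days the bracket is positive, so relief is understated. If use is unrelated to pain the bracket is zero.

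**2. Size.** Assumed inputs: 28 days (the shortest planned observation period), mean pain 5, lag-1 correlation 0.5, APS rounded and held within 0 to 10, true effect -1.0, and 8,000 simulated patients per cell. Rescue use is logistic (intercept -0.5), giving rescue on 38-43% of days. Use depends either on that day's average pain (close trigger) or on a quantity correlating 0.5 with it (weaker trigger). The weaker trigger fits breakthrough pain better, since Protocol 3.2 says: "This incident pain is an intermittent episode of extreme pain". Mean response by daily SD and by rise in log-odds of use per pain point:

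| Daily SD | Close, 0.75 | Close, 1.5 | Weaker, 0.75 | Weaker, 1.5 |
|---|---|---|---|---|
| 0.75 | -0.63 | -0.36 | -0.82 | -0.69 |
| 1.0 | -0.37 | 0.00 | -0.68 | -0.50 |
| 1.5 | +0.27 | +0.82 | -0.37 | -0.11 |

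- Repeat runs move these entries by 0.03 at most. With use unrelated to pain the response is -1.00.
- Milder dependence, log-odds 0.25 to 0.5 (odds ratio exp(0.25) = 1.28 to exp(0.5) = 1.65): -0.94 to -0.53 (weaker) and -0.87 to about -0.05 (close). No cell reverses.
- Overall, for log-odds 0.25 to 1.5: about -0.94 to -0.10 (weaker) and -0.87 to +0.82 (close).
- With rescue on 19-30% of days and log-odds 0.75 to 1.5: -0.82 to -0.08 (weaker) and -0.63 to +0.88 (close).
- At log-odds 0.75 to 1.5, both triggers together: a true effect of -2.0 gives -1.82 to -0.17 and never reverses on average; a true effect of -0.5 gives -0.31 to +1.33.

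A second calculation used independent days, a close trigger and rescue on about 30-37% of days. At SD 1.5 it gave -0.98, -0.46, +0.01 and +0.60 for odds ratios of 1.00, 1.28, 1.65 and 2.72 per point. The pattern is the same. At SD 2.0, outside the range above, the odds ratio of 1.65 already gave +0.68.

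**3. Effect on the planned output.** Adding the same constant to every patient's response changes only the intercept of a ridge model, so held-out residuals and correlations do not move. False prediction needs a baseline trait linked to daily pain variability or to how steeply rescue follows pain. A calculation built such a link in, with a true effect of -1.0 in everyone, 20 predictors and 80/20 splits. At 20-30 users of one drug, the false held-out correlation was at most 0.15 (trait correlating 0.6 with the driver, close trigger) and at most 0.05 with the weaker trigger. Pooled held-out R2 was below zero in every cell up to 60 users, and about 60 is the whole interim set.

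**4. Loss of true signal.** With true effects varying between patients (mean -1.0, SD 0.5), the correlation of true with measured effect was 0.74 (use unrelated to pain), 0.72 (weaker) and 0.67 (close).

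**5. When it applies.** If t is a single drug taken as rescue, or a class that the patient takes only as rescue, the patient enters the model and the bias arises. If t is a class that the patient also takes on schedule every day, t is present on all days and the patient falls outside the entry rule.

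**The case against.** The strongest reply is that the bias falls on a quantity the SAP does not plan to report. The objective is to find predictive factors, A3's table shows predictive performance, and nothing tabulates a mean on-off effect per drug or compares drugs. On the planned output the calculated effect is small even with trait links that neither document supports. All of this stands, and it limits the point to interpretation.

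Two further replies also stand. The dependence of rescue on average pain is assumed, and under mild dependence the response shrinks without reversing. And t may turn out to be a drug class, which removes some patients from the problem.

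The remedy can also be challenged. Limiting A3 to scheduled drugs could leave it with little data: the diary requires only rescue intake daily, and no passage says that prescription change dates are captured. Scheduled drugs changed for need are confounded in the same way. That is a good reason to keep the rescue models and label them, but not to leave them labelled as efficacy.

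A reader might go further and infer that A3 will show effective rescue drugs to be harmful, rank them unfairly against scheduled drugs, or distort the interim sample-size decision. The documents do not support these readings. Reversal needs particular assumed conditions, no ranking is planned, and no material distortion of the learning curve has been shown.

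**Conclusion.** The point holds as one about meaning. SAP 5.3 does not exclude rescue from t, and if rescue follows pain, the on-minus-off difference is biased towards no effect. Within the assumed range for a true effect of -1.0, the average is clearly above zero only with a close trigger, SD 1.5 and log-odds of 0.75 or more per point. Elsewhere it is attenuated, by anything from a few hundredths to the whole effect.

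This rests on the unstated premise that rescue is taken on worse days, and on assumed variability and steepness of use. The direction follows from the algebra once that premise is granted; the size cannot be taken from the documents. The importance lies between minor and should-fix.

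**What to change.** In SAP 5.3:

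- Define t as a drug or a class.
- Tag each A3 model as scheduled or rescue according to how t was taken.
- Keep the rescue models, but report them separately as exploratory, and state that their on-off difference is not interpreted as treatment efficacy.
- State that scheduled drugs started or stopped for need carry the same caveat.

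In SAP 5.4.1, report the learning curve with and without the rescue models. Report the share of diary days with rescue beside APS. Do not restrict A3 to scheduled drugs unless their on- and off-dates prove usable.

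The cost is some SAP wording, one tag per model, a second learning curve and a little more reporting. SAP 4.2 already lists rescue intake separately. Fewer models could then be called efficacy models, and need-driven confounding of scheduled drugs would be disclosed but not removed.

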This statistical analysis plan covers the interim and final analyses of the Oncopain study T2001-01. As specified in the study protocol, the interim analysis will be executed as soon as 60 patients have completed the study.

The primary objective of the complete study consists in finding predictive factors of pain management and analgesic treatment efficacy in patients suffering from CIBP (cancer-induced bone pain). The analyses necessary to achieve this objective are very complex to conduct, due to the complexity of the data available. Secondary objectives describe intermediate milestones which will be reached during these analyses.

An interim analysis is also planned for the validation of sample size and necessary items among the personality tests.

All statistical analyses related to the study will be the responsibility of DNAlytics or designee. They will be conducted on the full analysis set. This set includes all data from patients who have been screened and who completed the study (no drop-outs). No safety analyses will be conducted during the interim study. The safety analyses on the complete database will be performed by the sponsor and reported in the Clinical Study Report. Additional exploratory analyses of the data will be conducted as deemed appropriate.

All hypothesis tests will be conducted at a two-sided alpha level of 0.05, unless otherwise stated.

Name	Company	Role
[name]	DNAlytics	Study design, analysis implementation, reporting
[name]	DNAlytics	Study design, analysis review, reporting
[name]	DNAlytics	Study design, analysis and report review
[name]	Tools4Patient	Study design. As study sponsor representative, monitors data analysis progress.

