5.1.3 A1.3: Outlier detection and clustering

Population outliers will be detected through a principal component analysis (PCA) visualization, reported in Figure (1). The percentage of variance captured will be documented. The patients will be colored by their study center in order to detect possible differences among the centers.

Outliers might be removed for at least parts of the further analyses. Such cases will be documented.

A clustering procedure, namely an ensemble k-Means, will be applied in order to identify subgroups of patients with intra-group similar variables at baseline, and inter-group different variables at baseline. Table (tab-v1-clustering-desc) will report per-cluster univariate statistics (median, first and third quartiles) for all variables used in the clustering procedure.

A1.4: Correlation analysis 5.1.4

The correlation between each variable (personality traits and sociodemographic variables) and the pain at baseline (APS, WPS, BPI severity, interference and QLQ-C30) will be assessed. Statistical tests for non-zero Spearman's correlation will be used. For categorial variables, exact Fisher tests will be used. Correction for multiple testing will be applied. Results will be reported in Table (tab-v1-correlations) and Figure (2). Scatterplots of the significant correlations will be produced. Figure (3) will detail the correlations within pain assessment variables and Figure (4) the correlations between personality traits and pain assessment.

5.2A2: Evolution of daily pain and treatments

Pain evolution will first be analysed on its own (secondary objective 3, i.e. without linking it to the evolution of treatments). Then, the evolution of analgesic therapies are studied, as well as their correlation with pain evolution. Due to the complexity of treatments combinations for each patient and their frequent adaptation during the follow-up period, this analysis will be made on a simple summary of the therapy evolution. Finally, the interest of each variable characterizing the patient at baseline is evaluated for its relation with the pain evolution profile.

A2.1: Summary of individual pain evolution 5.2.1

Feature extraction will be performed in order to summarize each per-patient APS evolution curve into 3 meaningful variables:

- mean APS value
- linear trend of APS
- variability of APS around trend

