5.4.1 I1: Sample size computation for the prediction of treatment efficacy

For computing the necessary sample size, a *learning curve* will be evaluated for the analysis in A3. This analysis will first be run on all patients available in the interim database extract, and the average per-treatment performance will be computed. Then a random sample of 90% of the patients will be drawn and the same analysis will be repeated. And similarly with decreasing sample size.

This will lead to a "learning curve" showing the variation of predictive performance wrt to sample size and shown in Figure (7). An extrapolation of the curve will be performed in order to estimate the expected performance obtained in the final analysis using all 140 samples. A confirmation of infirmation of the number of patients to be included in the study will be made based on this estimation

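### The A3 target is called a treatment effect, but for a drug started once and kept it also carries the patient's own pain trend, which held-out testing cannot detect

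*SAP*

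**What the plan says.** SAP section 5 assigns this analysis to the main question: "A3: Prediction of treatment efficacy, covering the primary objective". Section 5.3 fits one ridge model per treatment, with baseline characteristics as predictors. The response is "Per-patient treatment effect, as measured by the average difference of daily APS between the days with and without treatment t", and the patients are defined by "Scope: patients having received treatment t on some but not all days". No adjustment for day, earlier pain or other analgesics is named. Performance comes from 200 random 80/20 splits: "Table (tab-pred-perf) will report the average predictive performance on the test sets for each treatment, in terms of relevant statistics".

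Elsewhere the SAP treats pain as moving over time. A2.1 fits a linear APS trend to each patient. A2.3 then relates traits to it: "For each feature from the patient characteristics at V1, the correlation will be computed with the linear trend of pain evolution defined in A2.1". I2 repeats this at the interim.

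Treatment is not randomised. Protocol 4.1 has the investigator treat and review according to the patient's needs, with reviews at Visit 1B and at the optional intermediate visit as well as at enrolment. Protocol 7.2.2 allows rescue medication. SAP 5.2 explains its simplified treatment summary thus: "Due to the complexity of treatments combinations for each patient and their frequent adaptation during the follow-up period".

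I1 reuses A3 performance for the sample size: "An extrapolation of the curve will be performed in order to estimate the expected performance obtained in the final analysis using all 140 samples".

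**The concern.** When a drug is started partway through and continued, all off-days come before all on-days. Any drift in pain over follow-up then enters the on/off difference and is counted as drug effect.

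A drift common to all patients would only move the model's intercept. A drift that differs between patients is more serious, because a trait related to it becomes a predictor of the A3 target even if the drug does nothing. A2.3 and I2 look for exactly such traits, so the SAP regards the link as plausible, but A3 does not carry the trend forward.

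Held-out testing guards against overfitting, not against a target that measures something else. Predictable pain course could therefore be reported as predictable efficacy of a named drug.

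**Working it through.** The plan gives no figure for this point, so there is none to reproduce.

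**1. The slope term.** Let APS on day d be a + b·d + D·on(d), where b is the background slope apart from the drug and D is an immediate, additive drug effect. The drug is off on days 1 to k and on from k+1 to T.
- Mean on-day: (k + 1 + T)/2
- Mean off-day: (k + 1)/2
- Difference: T/2, whatever the value of k
- A3 target: D + b·T/2. If the drug is instead stopped once: D − b·T/2.

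The values of T come from Protocol 8.5.4. Day 29 is the suggested Visit 2 in Table 1. Day 36 is the suggested Visit 2 in Table 2 (8 + 28). Day 71 is the latest allowed Visit 2 in Table 2 (29 + 42). The T/2 gap was confirmed for every possible start day.

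| T | T/2 | Target for an inert drug if b = −0.03/day (assumed) |
|---|---|---|
| 29 | 14.5 | −0.44 |
| 36 | 18.0 | −0.54 |
| 71 | 35.5 | −1.07 |

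**2. Other patterns (T = 28).** The slope multiplier is −14 for a drug stopped once, 0 for use on days 8 to 21 only, and +1 for alternate days. Random intermittent use averages 0. The problem therefore belongs to treatments whose changes run mainly in one direction.

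**3. How far a trait could predict the target of an inert drug.** Assumptions, none from the documents: slope SD 0.03/day, daily SD 1.5, day-to-day autocorrelation 0.3, trait–slope correlation 0.5, midway start. With s = 0.03 × T/2 and e the standard error of the on/off difference, the large-sample correlation is 0.5·s/√(s² + e²):
- 29 days: s = 0.435, e = 0.73, giving 0.26
- 36 days: s = 0.54, e = 0.66, giving 0.32
- 71 days: s = 1.065, e = 0.48, giving 0.46

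**4. What is left in a real sample.** These are simulated ridge fits with held-out scoring. Every one of 140 patients starts the same inert drug once, and change days lie in the middle half of follow-up unless stated.
- 29 days: held-out r about 0.17 with 10 predictors and 0.10 with 50
- 71 days: about 0.37 with 10 and 0.26 with 50
- 29 days, 10 predictors, start at the end of Visit 1 (one off-day): about 0.06
- 29 days, 10 predictors, only 30 eligible patients: about 0.09
- Half the patients stopping rather than starting: −0.03 to 0.03
- Day-adjusted target: −0.04 to 0.04

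Having all 140 completers on one drug and 71 days of follow-up are both upper-end cases.

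**5. Price of adjusting for day.** With independent days of SD 1.5 and a midway start at 29 days, the per-patient SE is 1.5 × √(1/14 + 1/15) = 0.56. Adding day raises it to 1.11. At 36 days it goes from 0.50 to 1.00, and at 71 days from 0.36 to 0.71. With a single off-day at 29 days the raw SE is already 1.5 × √(1 + 1/28) = 1.53, and adjustment takes it to 1.61.

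**The case against.** The strongest reply accepts the algebra and disputes its practical weight.

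- **Predictors.** SAP 4.2 lists many more than ten candidates, which dilutes the signal. This stands.
- **Start day.** The treatment decision that every patient has is at the end of Visit 1 or 1A, after that day's APS is recorded. A drug started then and kept leaves one off-day and a weak signal, or none and the patient is out of scope. This stands.
- **Starts that depend on slope.** The signed offsets assume starting is unrelated to the background trend. If worsening patients are likelier to start, one assumed model moves the 29-day inert-drug mean from −0.44 to about −0.1 and makes the 71-day mean positive (about +0.3). The sign cannot be known in advance.
- **Frequent adaptation.** The documents nowhere say that start-once use is common. The result is conditional on it.
- **Existing cross-check.** A2.3 reports trait–trend correlations alongside A3. That helps only partly, because the A2.1 slope absorbs some drug effect and A3 is still labelled as efficacy.

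A reader might infer that A3 will produce false efficacy predictors, or that I1 will misjudge the number of patients. The documents support neither. The pattern of starts and the trait–slope link are unknown. SAP section 1 says "the interim analysis will be executed as soon as 60 patients have completed the study", and those patients are spread over all drugs, so the effect on I1 is probably small. A reader might also conclude that the day-adjusted target should replace the raw one. It should not: it is noisier, and after a flare-triggered start it can worsen the bias, because the high scores just before the start tilt the fitted trend upwards.

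Which record supplies daily use of prescribed analgesics is a separate question and is not argued here.

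**Conclusion.** The point holds in a limited form. A3 names as a treatment effect a quantity that, for a drug started or stopped once, mixes drug effect with background slope times plus or minus T/2. That identity is exact under a linear background trend and an immediate additive effect. It also follows directly from the design that the held-out 20% cannot reveal the mixture.

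What cannot be settled is how much this matters. Under the stated assumptions, held-out correlation for an inert drug runs from near zero to about 0.37, and the larger values need long follow-up, many eligible patients, few predictors, mid-course starts and mainly one-directional changes. Confidence is high that the adjustment is absent and moderate at best on its size. The main risk is in how A3 is interpreted. It should be fixed, because A3 carries the primary objective and the remedy is light.

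**What to change.** 1. Describe the A3 response, and the performance used in I1, as a within-patient association between on- and off-days, not as a treatment effect or efficacy.
2. Keep the raw target and add one sensitivity analysis of A3 that uses the per-patient on/off coefficient from a regression including day. State that it is noisier, removes confounding by need only in part, and can worsen bias after a flare-triggered start.
3. For each treatment, report eligible patients, numbers of starts and stops, and follow-up length.
4. If prediction appears only with the raw target, report that pain course and drug effect cannot be separated, and cross-check against A2.3. Do not reclassify the trait as a pain-course predictor, since a true efficacy predictor can be lost in the noisier version.

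The cost is SAP wording, one extra per-patient regression and some added table columns. SAP V1.3 is dated April 2017 and the interim transfer was estimated for May 2017, so on those dates the change could precede the interim data.

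The statistical cost is real. In one illustration (140 patients, 10 predictors, a true efficacy predictor unrelated to slope, drug effect mean −0.5 and SD 0.7, trait correlation 0.5), adjusting for day lowers held-out r from 0.23 to 0.15 at 29 days but raises it from 0.16 to 0.23 at 71 days. That is why both versions should be shown.
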